# 8.2 Cataract Extraction and IOL Replacement

If the subject meets all criteria at the Baseline visit, he or she will be scheduled for surgery within 60 days of completing the Baseline visit. In the period between the baseline visit and the surgery date, the patient may be re-started on hypotensive medications after determination of the washed out diurnal IOP. Cataract replacement surgery will be done with phacoemulsification using standard techniques. IOL's suitable for glaucoma subjects will be selected according to physician or subject preference.

If the subject meets all intraoperative eligibility criteria, randomization to either the *Hydrus* group or *iStent* group will be performed at the end of the cataract extraction and IOL implantation. Computer-generated randomization lists will be used, with separate randomization lists for each clinical site. The site will open the randomization envelope upon completion of an uncomplicated cataract extraction and IOL implantation. The subject will not be informed of the randomization assignment and all study personnel will be instructed to maintain the "masking" of the treatment assignments.

#### 8.3 Surgical Procedure

After the subject's randomization group is identified, the subject shall receive either one *Hydrus* or *iStent*.

If the subject has been randomized to receive the *iStent*, the implant procedure should be performed according to the *iStent* Instructions for Use.

Implant surgery of the *Hydrus* device will be performed in all qualified study subjects randomized into the test arm. Surgery will be performed under either local or topical ophthalmic anesthesia.

Implantation of the Hydrus device will be performed after cataract extraction and IOL implantation as instructed below:

1. Position the subject's head for use of direct gonioprism lens.

- 2. Place gonioprism lens on the eye to establish a view of the angle. Use ophthalmic viscosurgical device (OVD) as a coupling agent. Verify angle structures including scleral spur and trabecular meshwork to determine target location. Remove gonioprism lens.
- 3. The corneal incision must be located four clock hours clockwise from the target location for right-handed access (opposite for left-handed access). If the corneal incision used for the cataract procedure is not viable for the introduction of the *Hydrus Implant*, make an additional 1.5mm incision in the corneal limbus. Use an oblique incision angled toward the target location.
- 4. Inject Healon GV or similar OVD into the anterior chamber unless similar OVD remains from cataract procedure. Verify eye is firm but do not overinflate.
- 5. Remove the Hydrus delivery device from the packaging and adjust the cannula orientation for proper hand position.
- 6. Advance *Hydrus Implant* slightly out of the cannula, dip in OVD and retract implant back into cannula.
- 7. Insert cannula through corneal incision, keeping needle curve parallel to iris to prevent touching iris, lens or cornea when passing across the anterior chamber.
- 8. Replace gonioprism lens on cornea to establish view of anterior chamber angle and Hydrus cannula tip.
- 9. Pierce the trabecular meshwork by aiming the cannula tip slightly uphill toward the pigment. After piercing, the cannula tip should slide gently into Schlemm's canal.
- 10. Advance the device slowly by rolling the advancement wheel. If resistance is felt, stop advancement, retract if necessary and readjust the cannula.
- 11. Visually confirm Hydrus implant windows entering the canal. The windows should be visible during advancement.
- 12. When advancement is complete, roll wheel backwards to remove core.
- 13. After core is removed, disengage the delivery system from the implant by slowly moving the cannula tip away from the canal and remove the cannula from the eye.
- 14. Verify inlet placement and adjust if necessary using a Sinskey hook.
- 15. Irrigate and aspirate the OVD from the anterior segment completely.
- 16. Close the corneal incision per normal practice and verify eye is re-pressurized.

#### 8.4 Perioperative Medication

A topical antibiotic and a topical steroid will be administered after surgery. The following dosing regimen is recommended:

- 1. Moxifloxacin 0.5% (Vigamox®), one drop four times per day commencing the day of the procedure and continued for one week postoperatively.
- 2. Prednisolone acetate 1.0% (Pred Forte®), one drop four times per day for one week; followed by one drop three times per day for one week; followed by one drop two times per day for one week; followed by one drop once per day for one week, then discontinue.

Medication to treat transient post-operative spikes in IOP resulting from the use of viscoelastic and surgical manipulation may be required in the immediate postoperative period.

# 8.5 Device Inventory

Each Hydrus Implant will be traceable via lot number. Lot numbers will be assigned according to date of manufacture and/or sterilization. Records of device shipments will be maintained at the Ivantis, Inc. facility in accordance with Ivantis Inc.'s Quality System and internal procedures. As only Hydrus Implant devices with CE mark clearance will be used in this study, device accountability records will not be required by the site.

# 8.6 Study Visits and Examination Schedule

All subjects will participate in defined follow-up visits through 24 months. A Case Report Form (CRF) shall be completed for each scheduled exam. Unscheduled or interim visits should also be recorded using the appropriate CRF.

#### **Screening Visit**

The subject must sign a subject informed consent prior to the commencement of any study related procedures. Initial eligibility will be determined at the Screening Visit. If the screening criteria are met, the subject will be considered enrolled in the study and will be instructed to discontinue the use of ocular hypotensive medications, according to Table 2, prior to returning for the Baseline Exam. Subjects not using an ocular hypotensive medication may be scheduled for the Baseline Exam up to 45 days after completing the Screening Exam. Ineligible subjects will be exited from the study. The reason for exit will be documented on the Study Summary Form for each enrolled subject.

The following information will be captured at this visit:

- Signed subject informed consent (if not done previously)
- Demographic information, medical history and ocular medications
- Bilateral best corrected visual acuity (Snellen)
- Bilateral manifest refraction
- Bilateral Humphrey 24-2 SITA standard visual field (All required visual fields will be obtained with a Humphrey automated perimeter using the 24-2 SITA standard threshold strategy.)
- Bilateral slit lamp biomicroscopy
- Bilateral IOP with Goldmann tonometer

NOTE: Any time IOP is performed, two measurements should be obtained for each IOP measurement; if these values are within  $\pm 2$  mmHg of one another, the mean of these two readings will be recorded on the CRF. If the first two measurements differ by more than 2 mmHg, a third measurement will be performed, and the median of the three measurements will be used.

- Bilateral dilated fundus examination and C:D ratio assessment\_Gonioscopy in the study eye (including Shaffer grading for all 4 quadrants)
- Bilateral central corneal pachymetry

#### Safety Visit

Between the screening visit and the baseline visit, the subject's IOP status may be checked at the discretion of the investigator. Data from this visit will not be collected unless an adverse event occurs. If during the washout period, the subject experiences an IOP spike of > 36 mmHg requiring the use of hypotensive medication or surgical intervention, the subject will be exited from the study.

# Baseline

The Baseline visit is performed following glaucoma medication wash-out, to confirm subject eligibility after medications are discontinued. The following information will be captured at this visit:

- Bilateral assessment of any changes in ocular medical history and medications
- Bilateral manifest refraction
- Bilateral ETDRS best-corrected visual acuity
- Bilateral slit lamp biomicroscopyNon-diurnal Goldmann tonometry, fellow eye only
- Diurnal Goldmann tonometry, study eye only, taken at 3 time points:
  - Time 1: 8:00 AM ( $\pm$  1 hour)
  - Time 2: 4 hours later ( $\pm 1$  hour) than Time 1
  - Time 3: 4 hours later ( $\pm 1$  hour) than Time 2.

Mean diurnal IOP will be computed from the three IOP time points. The mean diurnal IOP must be  $\ge 22$  and  $\le 36$  mmHg in order to qualify for the study.

#### Operative

Surgery will be scheduled after the subject successfully completes the baseline exam, but not more than 60 days after the date of the baseline exam. In the period between the baseline visit and the surgery date, the patient may be re-started on hypotensive medications after determination of the washed out diurnal IOP.

The following information will be collected at this visit:

- Randomization assignment
- Type of anesthesia
- •
- Clock hour location of Hydrus insertion
- Viscoelastic used
- Surgical complications
- Intraoperative adverse events (AEs)

#### **1 Day Postoperative**

This visit must occur on the first day postoperatively. The following information will be captured at this visit:

• Ocular medications

- Pinhole visual acuity
- Slit lamp biomicroscopy
- Goldmann tonometry at  $8:00 \text{ AM} \pm 1 \text{ hour}$
- Adverse events.

# 1 Week Postoperative $(7 \pm 2 \text{ days})$

The following information will be captured for the study eye, unless otherwise noted, at this visit:

- Ocular medications
- Manifest refraction
- ETDRS BCVA
- Slit lamp biomicroscopy
- Goldmann tonometry at 8:00 AM  $\pm$  1 hour
- Gonioscopy
- Adverse events.

#### 1 Month Postoperative $(30 \pm 7 \text{ days})$

The following information will be captured for the study eye, unless otherwise noted, at this visit:

- Ocular medications
- Manifest refraction
- ETDRS BCVA
- Goldmann tonometry at 8:00 AM  $\pm$  1 hour
- Slit lamp biomicroscopy
- Gonioscopy
- Adverse events.

# 3 Months Postoperative (90 $\pm$ 14 days)

The following information will be captured for the study eye at this visit:

- Ocular medications
- Manifest refraction
- ETDRS BCVA
- Humphrey 24-2 SITA standard visual field
- Slit lamp biomicroscopy
- Goldmann tonometry at 8:00 AM  $\pm$  1 hour
- Fundus examination and C:D ratio assessment
- Gonioscopy
- Adverse events

#### 6 Months Postoperative ( $180 \pm 21$ days)

The following information will be captured for the study eye, unless otherwise noted, at this visit:

- Ocular medications
- Manifest refraction
- ETDRS BCVA
- Humphrey 24-2 SITA standard visual field
- Slit lamp biomicroscopy
- Goldmann to nometry at 8:00 AM  $\pm$  1 hour
- Fundus examination and C:D ratio assessment
- Gonioscopy
- Adverse events.

# 12 Months Postoperative $(365 \pm 45 \text{ days})$

The following information will be captured at this visit:

- Ocular medications
- Bilateral manifest refraction
- Bilateral ETDRS BCVA
- Bilateral Humphrey 24-2 SITA standard visual field
- Bilateral slit lamp biomicroscopy Non-diurnal Goldmann to nometry, fellow eye only, at 8:00 AM  $\pm$  1 hour
- Diurnal Goldmann tonometry, study eye only, taken at 3 intervals:
  - Time 1: 8:00 AM ( $\pm$  1 hour)
  - Time 2: 4 hours later ( $\pm 1$  hour) from Time 1
  - Time 3: 4 hours later ( $\pm 1$  hour) from Time 2

#### NOTE:

- If the subject is not on medications in the study eye, then a diurnal measurement may be taken for the study eye at this visit.
- If the subject is on medications in the study eye, the subject's IOP should be checked at a single time period, and if appropriate, begin wash out of medications in the study eye according to Table 2. After the appropriate time period, a diurnal IOP should be obtained for the study eye.
- All IOP measurements must be performed within the Month 12 protocol specified window.
- If the principal investigator deems wash out inappropriate due to safety reasons, a clinical justification must be documented on the appropriate case report form.
- Bilateral dilated fundus examination and C:D ratio assessment
- Gonioscopy for study eye
- Bilateral central corneal pachymetry
- Adverse events

# 18 Months Postoperative ( $540 \pm 28$ days)

The following information will be captured for the study eye, unless otherwise noted, at this visit:

- Ocular medications
- Manifest refraction
- ETDRS BCVA
- Slit lamp biomicroscopy
- Goldmann tonometry
- Dilated fundus examination and C:D ratio assessment
- Gonioscopy
- Adverse events.

#### 24 Months Postoperative $(730 \pm 45 \text{ days})$

The following information will be captured at this visit:

- Ocular medications
- Bilateral manifest refraction
- Bilateral ETDRS BCVA
- Bilateral Humphrey 24-2 SITA standard visual field
- Bilateral slit lamp biomicroscopy
- Non-diurnal Goldmann to nometry, fellow eye only, at 8:00 AM  $\pm$  1 hour
- Diurnal Goldmann tonometry, study eye only, taken at 3 intervals:
  - o Time 1: 8:00 AM ( $\pm$  1 hour)
  - Time 2: 4 hours later ( $\pm 1$  hour) from Time 1
  - $\circ$  Time 3: 4 hours later (± 1 hour) from Time 2

NOTE:

- If the subject is not on medications in the study eye, then a diurnal measurement may be taken for the study eye at this visit.
- If the subject is on medications in the study eye, the subject's IOP should be checked at a single time period, and if appropriate, begin wash out of medications in the study eye according to Table 2. After the appropriate time period, a diurnal IOP should be obtained for the study eye.
- All IOP measurements must be performed within the Month 24 protocol specified window.
- If the principal investigator deems wash out inappropriate due to safety reasons, a clinical justification must be documented on the appropriate case report form.
- Bilateral dilated fundus examination and C:D ratio assessment
- Gonioscopy for study eye
- Bilateral central corneal pachymetry
- Adverse events.

The procedures associated with each study visit are outlined and summarized in **Appendix** 1 (Schedule of Events and Procedures).

#### **Unscheduled Visits**

Any visit to the clinical site, other than those specified in the protocol, will be documented as an unscheduled visit. Examples of unscheduled visits may include a subject complaint regarding the study eye and/or treatment to the study eye is required or changed, or any other visit deemed necessary at the discretion of the clinician. The Investigator and/or qualified investigational staff will perform the procedures necessary to evaluate the study participant at these visits, and will record the visit in the subject's chart and on an interim CRF. No specific testing is required at interim visit.

# 8.7 Postoperative Ocular Hypotensive Medications

Since the study population is undergoing cataract surgery involving use of an ophthalmic viscoelastic agent and post-operative steroids, both of which are known to cause IOP elevation, use of glaucoma medications in the first month after surgery is expected in some cases. In these cases, additional visits may be performed to assess IOP, and medications discontinued if the subject's condition allows.

Long-term medical therapy may be implemented or additional surgical measures may be performed at any time during the study at the Investigator's discretion in the event it is required. The primary concern of the Investigator and Sponsor at all times is the health and safety of the subjects.

A record of all medications added, discontinued or changed will be documented on the appropriate Case Report Form for each scheduled visit or on a Case Report Form for an Unscheduled (Interim) Visit, if necessary.

#### 8.8 Treatment of the Fellow Eye

The fellow eye should be treated within the site's standard of care. Any enrolled subject – regardless of randomization assignment – may receive CE-marked *Hydrus Implant* treatment as part of the standard of care to the fellow eye in conjunction with planned IOL implantation – following initial randomization and treatment of the assigned eye in the study.

#### 8.9 Subject Disposition

Subjects may be terminated (exited) from the study early due to:

- Screening failure,
- A threat to the subject's health emerges in the course of following study procedures,
- Inability to continue with the study, and
- Voluntary withdrawal.

Subjects who are terminated due to screen failure will not be followed beyond the date of screen failure. For safety reasons, randomized subjects who are terminated shall be followed until the planned end of study period. Terminated subjects will not be replaced. Notification of a subject's early termination should be made immediately to the sponsor and documented on the appropriate CRF.

Completed subjects are those subjects who have not been terminated from the study prior to completion of follow up.

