#### 6.3 Safety Analysis

All study subjects randomized in the study will be evaluated for safety outcomes. Frequency tabulations of safety outcomes will be performed at 1, 3, 6, 12, 18 and 24 months

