# 9.1 Protocol-defined Adverse Events

Adverse events as defined in this protocol include all ocular adverse events (AE) in the study eye. These events must be reported on the adverse event CRF. The Investigator must categorize each AE by degree of harm to the subject (mild, moderate, or severe), and the relationship to study device and implantation procedure (not related, possibly, probably, or definitely). Since there are no aspects of the study that can affect both eyes, only serious adverse events observed in the fellow eye will be captured on the case report form throughout the course of the study.

Ocular conditions or diseases that are chronic but stable and meet the inclusion and exclusion criteria should be recorded on the screening CRF under Ocular History. Changes in any chronic condition or disease that are consistent with natural disease progression are not considered AEs and will not be recorded on an AE CRF.

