# 9.7 Adverse Events Requiring Expedited Reporting

Investigators must report any events that meet any one of the following criteria to Ivantis within 48 hours of observing or learning of the event:

- Any adverse event with an outcome of death or blindness.
- Any Serious Adverse Event (SAE) that is device or procedure related.
- Any unanticipated adverse device effect (UADE), also called an unanticipated devicerelated adverse event.

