# APPENDIX 1: SCHEDULE OF EVENTS AND PROCEDURES (HYDRUS III REV C)

Procedure	SCREENING 	BASELINE 	SURGERY	1 DAY Postop	1 WEEK Postop	1 Month Postop	3 Months Postop	б Months Postop	12  Months Postop	18 Months Postop	24  Months Postop
Informed Consent	Х										
Demographics	х										
Medical History	х	х									
Medication Assessment	х	х	x	x	х	x	х	х	х	х	x
Randomization			х								
BCVA - Snellen	х										
Visual Acuity-Pinhole				х							
Manifest Refraction	х	х			х	х	х	х	х	х	х
BCVA (ETDRS)		х			х	х	х	х	х	х	х
Goldmann Tonometry	Х	X 		Х	Х	х	Х	Х	X 	Х	X 
Pachymetry CCT	X								х		Х
Gonioscopy (study eye)	X				Х	Х	Х	Х	Х	Х	Х
Slit Lamp Exam	X	Х		Х	Х	Х	Х	Х	Х	Х	Х
Humphrey 24-2 SITA Standard	Х						х	х	х		х
Fundus Exam/C:D Ratio	Х						х	х	х	х	х
Adverse Event Assessment			х	х	х	х	х	х	х	х	х

At the Screening Visit, Baseline Visit, 12 Month and 24 Month postoperative visits, all assessments will be performed for both eyes.

Following washout of hypotensive medication(s), three IOP measurements will be performed at 8:00 AM (± 1 hour), 4 hours (± 1 hour) later, and again 4 hours (± 1 hour) later.

A Safety visit during the washout period between the Screening and Baseline visits is optional.

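### Washout and pre-randomization surgical events in subjects exited before randomization need not be followed to an outcome and lie outside the stated safety evaluation

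*Combined protocol and SAP*

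**What the plan says.** **Exposure.** Under 8.1 and the Screening Visit text in 8.6, a subject counts as enrolled once the initial screening criteria are met. Any ocular hypotensive medication is then stopped for the Table 2 period, 7 to 28 days depending on the drug. Both 8.1 and the Safety Visit text in 8.6 foresee a pressure spike above 36 mmHg during this time.

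**Follow-up after exit (8.9).** "Subjects who are terminated due to screen failure will not be followed beyond the date of screen failure". The next sentence reads "For safety reasons, randomized subjects who are terminated shall be followed until the planned end of study period". Screening failure is one of four listed reasons for termination. Another is "A threat to the subject's health emerges in the course of following study procedures". For subjects not yet randomized who leave for a reason other than screening failure, 8.9 sets no follow-up.

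**Capture.** The Safety Visit during washout is optional. Its data rule is "Data from this visit will not be collected unless an adverse event occurs". Section 9.1 requires ocular adverse events in the study eye to go on the adverse event form and does not limit this to randomized subjects. The Appendix 1 row "Adverse Event Assessment" has its first mark at Surgery.

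**Causality and expedited reporting.** Section 9.1 grades "the relationship to study device and implantation procedure (not related, possibly, probably, or definitely". Apart from death, blindness and unanticipated device effects, 9.7 expedites "Any Serious Adverse Event (SAE) that is device or procedure related".

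**Analysis (6.3).** "All study subjects randomized in the study will be evaluated for safety outcomes". Tabulations are planned at 1, 3, 6, 12, 18 and 24 months.

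**The concern.** The washout is imposed by the study, and the protocol itself anticipates that it may raise pressure enough to need medication or surgery. The subjects in whom this happens are the ones most likely to leave before randomization. For them the plan does not require anyone to find out how the event ended, and the stated safety evaluation does not include them.

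The same applies to cataract surgery. Section 8.2 opens the randomization envelope only after an uncomplicated extraction and lens implantation. The cataract complications listed in 9.3 can therefore keep an eye out of the randomized population.

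What is at stake is the account of risk from study participation. A report built on 6.3 would describe safety from randomization onward and leave out the washout and surgical events that led to exit. The comparison of the two implants is not affected, because both kinds of exit come before allocation.

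**Working it through.** **1. Trace a subject with a washout event.**

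| Step | What the plan provides | Where |
|---|---|---|
| Enrolled, medication stopped | 7 to 28 days by drug | 8.1, Table 2 |
| Check during washout | Optional visit; data kept if an adverse event occurs | 8.6 Safety Visit |
| Check at end of washout | Required examination: history and medication changes, acuity, slit lamp, three-point pressure; no adverse event item | 8.6 Baseline |
| Scheduled adverse event assessment | 9 of 11 schedule columns, from Surgery onward; none at Screening or Baseline | Appendix 1 |
| Event form | Required for study-eye ocular events | 9.1 |
| Exit | Reason documented; early termination notified to the sponsor | 8.6 Screening Visit, 8.9 |
| After exit, as screening failure | No follow-up beyond that date | 8.9 |
| After exit, as health threat, not randomized | Nothing stated | 8.9 |
| Safety evaluation | Randomized subjects only | 6.3 |

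Under either exit category, follow-up of an open event is not required. Under both, the subject is outside the stated evaluation.

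**2. Trace a subject with a surgical complication before randomization.** The Operative visit collects surgical complications and intraoperative adverse events, and Appendix 1 marks assessment at Surgery, so the event is recorded. The subject is not randomized (8.2), so 6.3 does not cover the event and the follow-up duty in 8.9 does not apply.

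**3. Size of the group outside the evaluation.** Section 8.1 gives about 100 enrolled and about 30% lost on pre- or intra-operative entry criteria.

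- The plan's own figure: 100 × (1 − 0.30) = 70 randomized, which reproduces. Not randomized: 100 − 70 = 30.
- Section 4.0 gives about 150 randomized, and 6.2 agrees (2 × 75 = 150). At the same 30% loss: 150 / 0.70 = 214.3, so about 214 enrolled and 214 − 150 = 64 not randomized.

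Both counts are upper bounds on subjects exited with a washout event. The 30% also covers eyes outside the 22 to 36 mmHg Baseline range, intraoperative failures and possibly subjects who were never on medication. The documents give no rate of washout events, so no expected number can be derived.

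**4. Text that conflicts.** Section 8.1 has a subject with a spike treated and leaves withdrawal open for consideration; the Safety Visit text in 8.6 makes exit the stated result. The two passages must be reconciled. So must the 70 randomized in 8.1 and the 150 in 4.0.

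**The case against.** Several stronger readings are tempting, and the documents do not support them.

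- *Washout harm goes unrecorded.* It does not. The Safety Visit rule keeps data when an adverse event occurs, 9.1 makes the event form mandatory for study-eye events, and exits are documented and notified. What is missing is a scheduled assessment, an outcome and a tabulation.
- *The optional visit is the only check.* The Baseline examination is required and falls at the end of washout. A subject exited earlier does not reach it, and it carries no adverse event item.
- *The plan bars follow-up of everyone exited for a washout spike.* The sentence in 8.9 covers screening failure, and no passage calls a spike exit a screening failure. For a health-threat exit before randomization, 8.9 is silent. Section 8.1 also says the subject will be treated. Silence still leaves follow-up optional, and treatment does not ensure that the outcome is recorded.
- *A serious washout event cannot be expedited.* Section 9.7 does not define procedure. Taking it to mean implantation only, by analogy with 9.1, is plausible but not stated.
- *There may be 88 unobserved days before the first assessment (28 + 60).* The Baseline examination lies within that interval, and medication may be restarted after it.
- *Thirty or 64 subjects are harmed.* These counts are exits for any entry criterion.

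Two further objections carry weight. Section 6 appears shortened in the public text, so a fuller safety section may exist. And the washouts before Months 12 and 24 concern randomized subjects, who have scheduled adverse event assessment and are in the safety evaluation; there only the missing causality category remains. Neither objection touches 8.9 or Appendix 1, which establish the follow-up and scheduling gaps on their own.

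**Conclusion.** The point holds in limited form. Observed washout events in the study eye are to be recorded, but none is actively sought by a scheduled assessment before Surgery. The outcome of such an event in a subject exited before randomization need not be ascertained, and the event is not in the stated safety evaluation. Surgical complications that prevent randomization are recorded but fall outside the same evaluation.

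About 30% of enrolled subjects are outside that evaluation: about 30 of 100, or about 64 of 214. The number with a study-related event among them is unknown and may be small. The conclusion rests on 6.3 as published and assumes, for the larger count, that the 30% loss in 8.1 also applies to 150 randomized.

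This is a gap in safety reporting that should be closed. It does not bias the randomized comparison.

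**What to change.** 1. **Section 8.9.** State that a subject exited after washout has begun, or during surgery, has any open study-related adverse event followed for safety data until it is resolved or stable, whatever the exit category, with the outcome on the adverse event form.
2. **Appendix 1 and the Baseline list in 8.6.** Add adverse event assessment at Baseline.
3. **Section 6.3.** Add a descriptive tabulation of adverse events from the start of washout for all enrolled subjects, separate from the comparison by arm.
4. **Sections 9.1 and 9.7.** Add *study-required washout* as a relationship category, and make clear that procedure-related in 9.7 includes it.
5. **Reconcile** 8.1 with the Safety Visit text on exit after a spike, and 8.1 with 4.0 on the number randomized. The sponsor should decide these; no rule for handling spikes is proposed here.

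The cost is protocol wording, one schedule mark, one form category, one extra table, and brief follow-up contact for the exited subjects who have an open event.
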